Procedure	Screening a			Inte	rvention	period ((28-day	cycles)				Post-in	tervent	ion follo	ow-up peri	od	Details in CSP section or appendix
	Scr		Cycl	es 1-2			Cycle 3	3	C4-on	wards	ntinued tment)	(# (follow- after las	_	al ftil W)	
Cycle Day	-21 to -1	Day 1	Day 7	Day 8	Day 15	Day 1	Day 7	Day 8	Day 1	Day 8	Study Treatment Discontinued (last dose of study treatment)	30 days	60 days	90 days	180 days (6 months)	Progression/Survival Follow-up (Q8W until 18 months, then Q12W)	
Visit window (± days)	-	-	-	-	± 1	± 3	-	± 1	± 3	± 1	Study Ti	± 3	± 7	± 7	±7	Prog Follo 18 mc	
ECOG performance status ¹	X	X		X		X		X	X		X	X	X	X	X	X	Section 8.2.4
Hepatitis B and C and HIV screening	X																Sections 5.1 and 8.2.5
Safety laboratory assessments (clinical chemistry including TSH, haematology, urinalysis ^{f, k, m})	X	X		X	X	X		X	X	X	X	X	Х	X			Section 8.2.5
Coagulation parameters ⁿ	X									X							Section 8.2.5
Pregnancy test (WOCBP only)°	X	X				X			X			X	X	X			Section 8.2.5
AE	X		+		t every v		nay be	X conducte	d by pho		tied to a vis		\rightarrow				Section 8.3
Concomitant medications	X		+		t every v		nay be	X conducte	d by pho	== ne if not	tied to a vis		\rightarrow				Section 6.5

Procedure	Screening a			Inte	rvention	period ((28-day	cycles)				iod	Details in CSP section or appendix				
	Scr		Cycl	es 1-2			Cycle 3	3	C4-on	wards	ntinued tment)	(#		ty follow-up s after last dose)		al frii W)	
Cycle Day	-21 to -1	Day 1	Day 7	Day 8	Day 15	Day 1	Day 7	Day 8	Day 1	Day 8	Study Treatment Discontinued (last dose of study treatment)	30 days	60 days	90 days	180 days (6 months)	Progression/Survival Follow-up (Q8W until 18 months, then Q12W)	
Visit window (± days)	-	-	-	-	± 1	± 3	-	± 1	± 3	±1	Study T	± 3	±7	± 7	± 7	Proj Folk 18 me	
Tumour imaging (RECIST 1.1; CT/MRI including brain scan at baseline) p, s	Xq					Tumour assessments will be conducted every 8 weeks (±1 week) after start of treatment (C1D1) up to 18 months, then every 12 weeks (±1 week) until objective disease progression per RECIST 1.1. If a patient discontinues without disease progression, RECIST tumour assessments will be performed every 8 weeks for 18 months, then every 12 weeks, thereafter.										Section 8.1.1	
CCI																	

Procedure	Screening a			Inte	rvention	period ((28-day	cycles)				Post-in	tervent	ion follo	w-up peri	od	Details in CSP section or appendix
	Sere		Cycl	es 1-2			Cycle 3		C4-on	wards	ntinued tment)	(# (/ follow- after las		al rtil W)	

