^a If screening assessments have been performed within 3 days prior to starting study intervention, they do not have to be repeated at Cycle 1 Day 1 if the patient's condition has not changed.

Written informed consent and any locally required privacy act document authorisation must be obtained prior to performing any protocol-specific procedures, including screening/baseline evaluations.

^c Submission of archival tumour tissue is mandatory for all patients. A minimum of 20 freshly cut unstained sections from the archival tumour block are accepted if tumour blocks cannot be submitted, however tumour tissue blocks are preferred.

Fresh tumour biopsies are mandatory, if medically feasible, in all patients with biopsiable disease at screening. However, if patients do not have disease suitable for biopsy, they are required to provide a tumour sample collected within 5 years prior to study entry. Optional on-treatment biopsies will be collected at Cycle 2 between Day 15 and Day 28 and at disease progression, only if a fresh tumour sample was provided at screening. Optional on-treatment biopsies are not required if a fresh tumour sample was not collected at screening. For sample collection details refer to Section 8.6 of the protocol.

- Submission of the cytological or histological report, and molecular report confirming BRAF mutation status is mandatory at screening. In addition, the investigator must confirm the type of PD-(L)1 resistance at screening and whether the LDH is normal or above upper limit of normal, in order to stratify the patients accordingly. Other genomic characteristics will be collected where known eg, NRAS, c-kit, PD-(L)1, NF1, MSI.
- Clinical laboratory assessment parameters are to be assessed at baseline on Day 1 (unless all screening laboratory assessments are performed within 3 days prior to Day 1) and full blood count result should be checked prior to dosing when assessed on a dosing day. Serum or plasma clinical chemistry (including LFT monitoring) and haematology may be performed more frequently if clinically indicated. Urinalysis should be performed at baseline (screening) and then as clinically indicated. Thyroid stimulating hormone testing is to be done at the timepoints indicated and also when clinically indicated (clinically suspecting immune-related hypo/hyper thyroidism). Free T3 or free T4 will only be measured if TSH is abnormal or if there is clinical suspicion of an AE related to the endocrine system.

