- Baseline demographics will include all prior treatments (start/stop dates, best response, treatment line, reason for treatment discontinuation and, if due to RECIST 1.1-defined disease progression, how progression was determined and dates of radiographic scans indicating disease progression) and disease stage at diagnosis and at study entry. Other genomic characteristics will be collected where known eg, NRAS, c-kit, PD-(L)1, NF1, MSI.
- h Collect data on prior anti-cancer therapies, including best response, setting (eg, adjuvant/metastatic), prior radiotherapy, and prior surgery. For the prior anti-PD-(L)1 regimen, also collect reason for discontinuation and details of scans indicating RECIST 1.1-defined disease progression, including anonymised copies of the scan reports.
- Additional physical examination will be performed, if clinically indicated.
- Triplicate ECGs at screening only. Subsequent ECGs should only be taken if clinically indicated.
- Whenever ECG, vital signs and blood draws are scheduled on the same day, it is recommended that the assessments occur in the following order: vital signs, ECG, and then blood draws. The timing of the ECG and vital signs assessments must allow for the blood draw (eg, PK blood sample) to occur at the scheduled time points.
- ECOG assessment also to be performed at initiation of subsequent anticancer therapy, where possible. In addition, ECOG performance status should be collected at initiation of subsequent anticancer therapy, if appropriate site staff are available to collect such information. Additional ECOG assessments may be performed (eg, on Day 15), if clinically indicated.
- Patients who develop a ≥ Grade 3 of anaemia, neutropenia, or thrombocytopenia during the treatment period will also need to have additional assessments on Day 15 (for combination of ceralasertib and durvalumab) until there is no evidence of ≥ Grade 3 anaemia, neutropenia, or thrombocytopenia for at least 2 cycles.
- ⁿ Coagulation will be performed at screening and as clinically indicated during subsequent visits.
- Women of childbearing potential only. Serum pregnancy test at screening, urine test at other time points up to 90 days after the last dose of study treatment. For country-specific requirements for Belgium and France see Appendices K 1.1 and K 1.2, respectively.

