- CT scans of the chest, abdomen, and pelvis (or MRI where CT is contraindicated) should be conducted every 8 weeks (±1 week) after the start of study treatment (Cycle 1 Day 1) up to 18 months, then every 12 weeks (±1 week) until objective disease progression as per RECIST 1.1, irrespective of treatment decisions. In the event of study treatment interruptions or delays, tumour assessments should proceed to schedule relative to Cycle 1 Day 1. Soft tissue or visceral progression observed by CT or MRI, according to RECIST 1.1, does not require a confirmatory scan. To confirm progression based on non-target lesions, additional scans or images/photographs may be required for submission for BICR.
- ^q Baseline contrast enhanced MRI brain scan assessment (or CT if MRI is contraindicated) for all patients at screening.

l	\sim	

CC

- For ceralasertib, PK sample will be collected in all patients at pre-dose (up to 1 hour prior) and 1 hour (± 30 min) post-dose on Day 7 of each cycle, for the first 3 cycles. For durvalumab, PK sample will be collected in all patients at pre-dose (up to 1 hour prior) and 1 hour (± 30 min) post-dose on Day 8 of each cycle, for the first 3 cycles. For non-dosing days, PK sample will be collected at similar times as dosing day.
- Immunogenicity sample for durvalumab to be collected at screening, then pre-dose on Day 8 of Cycles 1, 2, 3, and 4, then every 4 cycles, end of treatment, 90 days and 6 months (± 7 days) after last dose.
- w Every effort should be made to minimise the time between randomisation and starting treatment (ie, within 3 business days of randomisation).
- ^x Ceralasertib administered twice daily from Days 1 to 7 of each cycle. Durvalumab administered on Day 8 of each cycle.
- For ceralasertib, patients will be required to complete a dosing diary (e-diary) from Day 1 to Day 7 of each cycle, using an electronic device. The dosing diary must be reviewed by the designated study personnel on Day 1 of each cycle.
- CCI
- The device/e-diary should be fully charged, and checked that it is fully functioning, prior to the patient's first dosing visit. The site should ensure the patient is trained and understands how to use the PRO device/doing diary prior to the first use.
- bb Survival status collected 8 weekly reducing to 12 weekly after 18 months.
- Other anti-cancer therapies collected 8 weekly reducing to 12 weekly after 18 months. Off study treatment follow-up: subsequent anti-cancer therapies to be collected.

 Table 2

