 Ceralasertib Monotherapy (Main Study)

D I	Screening a		I	ntervent	tion per	riod (28	-day cyc	cles)		Pos	st-intervention follo	Details in CSP section or appendix	
Procedure	Scree	(Cycles 1	1-2	Cycle 3			C4-onwards		t itment)	Safety follow-up	Progression/Survival Follow-up	
Cycle Day	-21 to -1	Day 1	Day 7	Day 15	Day 1	Day 7	Day 15	Day 1	Day 15	Study Treatment Discontinued (Last dose of study treatment)	30 days after last dose	(Q8W until 18 months, then Q12W)	
Visit window (± days)	-	-	-	± 1	± 3	-	± 1	± 3	± 1	(Last	± 3	± 7	
Informed consent: main study ^b	X												Section 5 and Appendix A 3
Informed consent: genetic sample and analysis (optional) ^b	X												Section 5.1 and Appendix A 3
Archival tumour sample, mandatory ^c	X												Section 8.6.1
Fresh tumour biopsy	X			X (C2 only)						X (PD)			Section 8.6.1
Inclusion and exclusion criteria e, f	X	X											Sections 5.1, 5.2 and 5.4
Demography ^g	X												Section 5.1
Prior anti-cancer therapy h	X												Section 5.1
Full physical examination ^a	X	X			X			X		X	X		Section 8.2.1
Targeted physical examination ⁱ			X	X		X	X		X				Section 8.2.1

D	Screening a		I	ntervent	tion per	riod (28	-day cyc	cles)		Pos	Details in CSP section or appendix		
Procedure	Scree	(Cycles 1	l-2		Cycle			t itment)	Safety follow-up	Progression/Survival Follow-up		
Cycle Day	-21 to -1	Day 1	Day 7	Day 15	Day 1	Day 7	Day 15	Day 1	Day 15	Study Treatment Discontinued (Last dose of study treatment)	30 days after last dose	(Q8W until 18 months, then Q12W)	
Visit window (± days)	-	-	-	± 1	± 3	-	± 1	± 3	± 1	(Last	± 3	± 7	
Height	X												Section 8.2.1
Weight a	X	X		X	X		X	X	X	X	X		Section 8.2.1
Past and current medical conditions	X	X a											Sections 5.1 and 5.2
12-lead ECG ^{j, k}	X (Trip licat e)			As clinic	ally ind	icated;	single E0	CGs					Section 8.2.3
Echocardiogram/MU GA	X			As	s clinica	ılly indi	cated			X			Section 8.2.6.1
Vital signs k	X	X	X	X	X	X	X	X	X	X	X		Section 8.2.2
ECOG performance status ¹	X	X			X			X		X			Section 8.2.4
Hepatitis B and C and HIV screening	X												Section 5.1 and 8.2.5
Safety laboratory assessments (clinical chemistry including TSH, haematology, urinalysis) ^{f, k, m}	X	X	X	X	X	X	X	Х	X	Х	X		Section 8.2.5

Procedure	Screening a		I	ntervent	tion per	riod (28	3-day cyc	cles)		Pos	t-intervention follo	Details in CSP section or appendix		
	Scree	(Cycles 1	1-2	Cycle 3			C4-onwards		t itment)	Safety follow-up	Progression/Surviva Follow-up		

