- Patients who develop a ≥ Grade 3 of anaemia, neutropenia, or thrombocytopenia during the treatment period will also need to have additional assessments on Day 7 (for ceralasertib monotherapy) until there is no evidence of ≥ Grade 3 anaemia, neutropenia, or thrombocytopenia for at least 2 cycles.
- ⁿ Coagulation will be performed at screening and as clinically indicated during subsequent visits. For country-specific requirements for Belgium see Appendix K 1.1.
- Women of childbearing potential only. Serum pregnancy test at screening, urine test at other time points up to 30 days after the last dose of study treatment. For country-specific requirements for Belgium and France see Appendices K 1.1 and K 1.2, respectively.
- Computed tomography scans of the chest, abdomen, and pelvis (or MRI where CT is contraindicated) should be conducted every 8 weeks (±1 week) after the start of treatment (Cycle 1 Day 1) up to 18 months, then every 12 weeks (±1 week) until objective disease progression as per RECIST 1.1, irrespective of treatment decisions. In the event of treatment interruptions or delays, tumour assessments should proceed to schedule relative to Cycle 1 Day 1. Soft tissue or visceral progression observed by CT or MRI, according to RECIST 1.1, does not require a confirmatory scan. To confirm progression based on non-target lesions, additional scans or images/photographs may be required for submission for BICR.
- ^q Baseline contrast enhanced MRI brain scan assessment (or CT if MRI is contraindicated) for all patients at screening.
- s CC
- t CC
- \overline{PK} samples will be collected in all patients at pre-dose (up to 1 hour prior) and 1 hour (± 30 min) post-dose on D7 of each cycle, for the first 3 cycles.
- Every effort should be made to minimise the time between randomisation and starting treatment (ie, within 3 business days of randomisation).

- w Ceralasertib administered twice daily from Days 1 to 7 of each cycle.
- For ceralasertib, patients will be required to complete a dosing diary (e-diary) from Day 1 to Day 7 of each cycle, using an electronic device. The dosing diary must be reviewed by the designation study personnel on Day 1 of each cycle.
- y CCI
- The device/e-diary should be fully charged, and checked that it is fully functioning, prior to the patient's first dosing visit. The site should ensure the patient is trained and understands how to use the PRO device/dosing diary prior to the first use.

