4.3.1 Ceralasertib Monotherapy Dose Rationale

The dose of ceralasertib selected for this study (240 mg BD) is primarily based on the clinical results observed in the HUDSON study (D6185C00001), with supportive data on preclinical, translational and clinical pharmacology data/modelling from Study 4 (D5330C00004).

Preliminary PK observations from Study 4 (D5330C00004) showed CCI dose-proportional increase in exposure, where the plasma concentrations following a single dose at 320 mg QD were CCI to that observed at 240 mg QD CCI % overlap in AUC), suggesting the need to change to BD schedules in order to increase ceralasertib exposure beyond the dose of 240 mg QD.

The dose of ceralasertib as monotherapy 240 mg BD for 7 days in 28-day cycles is based on clinical safety and tolerability (mainly bone marrow safety outcomes) and clinical PK/PD data. The dose level of 240 mg BD is predicted to maintain ceralasertib concentrations above the estimated concentration of an inhibitor where ATR catalytic activity is reduced by 90% (IC90) threshold for hours in ceralasertib based on simulations from a preliminary population PK model, and hence, it achieves maximum IC90 daily coverage. In addition, 1-week ceralasertib dosing maximises cytotoxic T-cell (CD8+/Ki67+) proliferative burst (by minimising the time in which proliferative T-cells are depleted) during the three-week off-treatment period, potentially promoting upregulation of PD-(L)1 which can be subsequently blocked with durvalumab to enhance anti-tumour T-cell responses.

Considering emerging PK data from ongoing studies, there is no evidence to indicate any ethnic sensitivity in Asian patients compared to Western patients.

The choice of ceralasertib schedule is supported by preclinical data in syngeneic mouse tumour models in which an intermittent dosing schedule for ceralasertib is most efficacious in terms of balancing the direct anti-tumour effects, the potential for priming an IFN-mediated immune response and dynamic modulation of the tumour immune microenvironment (see ceralasertib IB). An intermittent schedule is also supported by a population PK-PD model describing ceralasertib-induced thrombocytopenia and neutropenia, which showed that at least two-week off-treatment period is needed for platelet/neutrophil recovery. This same model also demonstrated that haematological toxicity is reduced with a 7-day schedule compared to 14-day schedule of ceralasertib.

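### After Cycle 2 the two arms have routine blood counts on different cycle days, so by-arm tables of graded cytopenia are not like for like

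*Protocol*

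**What the plan says.** In Section 1.3, haematology falls under the row "Safety laboratory assessments (clinical chemistry including TSH, haematology, urinalysis" in both main-study tables.

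- Table 1 (combination) marks that row on Days 1, 8 and 15 in Cycles 1-2, then on Days 1 and 8 in Cycle 3 and from Cycle 4. It has no Day 15 column after Cycle 2.
- Table 2 (monotherapy) marks it on Days 1, 7 and 15 in Cycles 1-3, then on Days 1 and 15 from Cycle 4.

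Ceralasertib dosing days are the same in both arms. The Table 1 footnote reads "Ceralasertib administered twice daily from Days 1 to 7 of each cycle. Durvalumab administered on Day 8 of each cycle", and Table 2 has the same seven ceralasertib days.

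Two provisions add counts. After a Grade 3 or worse anaemia, neutropenia or thrombocytopenia, combination patients "will also need to have additional assessments on Day 15 (for combination of ceralasertib and durvalumab) until there is no evidence", while monotherapy patients "will also need to have additional assessments on Day 7 (for ceralasertib monotherapy) until there is no evidence". In both cases this runs until the patient has been clear for at least two cycles, and Section 6.6 repeats the rule. In addition, "haematology may be performed more frequently if clinically indicated".

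On recovery, Section 4.3.1 cites a model showing that "at least two-week off-treatment period is needed for platelet/neutrophil recovery".

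On analysis, Section 9.4.3.1 tabulates adverse events by treatment arm, including Grade 3 or worse, and Section 9.4.3.2 calculates CTCAE laboratory grades from the values collected. The Synopsis states that safety is descriptive.

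**The concern.** A laboratory grade can be assigned only on a day when blood is drawn. If two arms receive the same myelosuppressive drug on the same days but are counted on different days, their grade tables reflect the sampling as well as the toxicity. Section 2.3.1.1 lists anaemia, neutropenia and thrombocytopenia as identified risks of ceralasertib, and Section 2.3.1.2 lists immune thrombocytopenia among the durvalumab risks. These are the rows that a reader will compare across the two columns. Nothing in the Protocol warns that the columns were sampled on different days after Cycle 2.

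**Working it through.** The Protocol states no figure on this point, so there is none to reproduce.

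**1. Routine count days and gaps.** Days are read from Tables 1 and 2. The next Day 1 is Day 29 of a 28-day cycle, and a gap is the difference between successive count days.

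| Cycle | Combination: days (gaps) | Monotherapy: days (gaps) | Longest gap, combination vs monotherapy |
|---|---|---|---|
| 1-2 | 1, 8, 15 (7, 7, 14) | 1, 7, 15 (6, 8, 14) | 14 vs 14 days |
| 3 | 1, 8 (7, 21) | 1, 7, 15 (6, 8, 14) | 21 vs 14 days |
| 4 onwards | 1, 8 (7, 21) | 1, 15 (14, 14) | 21 vs 14 days |

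With the visit windows (Day 8 ± 1, Day 1 ± 3), the combination gap can reach (29 + 3) − (8 − 1) = 25 days. From Cycle 4 each arm has two routine counts per cycle, and Day 1 is the only day they share.

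**2. What the conditional counts add.** Day 15 is already routine for the combination in Cycles 1-2, so the trigger adds something only from Cycle 3. It can be set off by a Grade 3 or worse result in Cycles 1-2, or on a later Day 1 or Day 8. It cannot detect a first fall that begins after Day 8 and recovers before the next Day 1. In the same way, the monotherapy Day 7 trigger adds something only from Cycle 4. Counts taken when clinically indicated depend on something prompting them.

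**3. Position of the gap relative to recovery.** Dosing ends on Day 7, and 7 + 14 = 21. Platelets and neutrophils are therefore expected to recover on about Day 21 or later. A fall after Day 8 can lie wholly inside the Day 8 to Day 29 gap, but Section 4.3.1 gives only a lower bound. It does not show that recovery is complete by Day 29.

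**4. Illustration of detection.** Assumptions, none of them from the Protocol: onset is uniform over the stated window, an episode lasts 7 days, and it is recorded if a routine count falls within it.

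| Assumed onset | Cycles 1-2, combination vs monotherapy | Cycle 4 onwards, combination vs monotherapy |
|---|---|---|
| Days 4-8 | 100% vs 75% | 100% vs 0% |
| Days 4-15 | 100% vs 91% | 36% vs 64% |
| Days 8-15 | 100% vs 100% | 0% vs 100% |
| Days 9-20 | 55% vs 55% | 0% vs 55% |

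If each episode instead lasts until Day 21, the Cycle 4 figures become:

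- Onset Days 4-8: 100% vs 100%, since every episode then spans both Day 8 and Day 15.
- Onset Days 4-15: (8 − 4)/11 = 36% vs 100%.
- Onset Days 9-20: 0% vs (15 − 9)/11 = 55%.

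The arms are close in Cycles 1-2 under every 7-day assumption except the earliest onset. From Cycle 4 they can diverge in either direction. Monotherapy never detects less if episodes last until Day 21, but that duration is assumed.

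**The case against.** The strongest objection is that a reader might infer that the combination arm will record fewer and milder cytopenias, and the documents do not support that. No nadir day is given, and the recovery time is a lower bound that covers platelets and neutrophils but not anaemia. Monotherapy has its own blind spot from Cycle 4, as the first row of the illustration shows. This stands, so no direction is claimed.

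A reader might also convert the gap into a share of follow-up. The 7.1-month median PFS cited in Section 4.2 gives 7.1 × 30.4375 / 28 = 7.7 cycles, of which (7.7 − 2) / 7.7 = 74% follow Cycle 2. That does not measure bias. Section 9.4.3.1 counts patients, not cycles, so a patient detected in Cycles 1-2 is already counted. The figure is also PFS rather than time on treatment, from a 30-patient study that used a 14-day ceralasertib schedule.

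Nor should the monotherapy arm be read as designed for a toxicity comparison. Section 4.2 frames it around activity, Section 9.1 plans no formal hypotheses, and safety is descriptive. This removes any claim about a biased test. It does not make two differently sampled columns comparable.

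The difference may be deliberate. Table 3 also moves biopsy sub-study patients to Days 1 and 8 from Cycle 2, and visit days follow the administration schedules. The dose-modification table in Section 6.6 is not legible in the public document, so further monitoring there cannot be excluded. A deliberate schedule still has this consequence for the tables.

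Finally, table layouts usually belong to the SAP. That is true of the remedy, but the unequal count days are fixed in the Protocol.

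**Conclusion.** The point holds in a limited form. After Cycle 2 the routine count days differ, with a longest gap of 21 days in the combination arm against 14 in monotherapy, and from Cycle 4 no post-dose count day is shared. The conditional Day 15 count narrows the combination gap but cannot reveal a first transient fall between Day 8 and the next Day 1. By-arm laboratory grades, and the adverse events that depend on them, are therefore not like for like after Cycle 2.

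Under-recording in the combination arm is plausible, but neither its direction nor its size is established. The schedule facts rest on the tables alone. The detection percentages rest on assumed onset and duration and show only that the comparison is sensitive to them. This is an inexpensive improvement to reporting; it touches no efficacy conclusion.

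**What to change.** 1. Add a by-arm summary of CTCAE-graded haematology and cytopenia adverse events restricted to Cycles 1-2, where routine counts fall on Days 1, 7 or 8, and 15 in both arms. Show it beside the all-cycle table, and label the all-cycle table as sampled on different days by arm after Cycle 2. This needs no new data, so the closure of recruitment does not matter. It costs one table and one footnote, and the matched summary loses later-onset events, which is why the all-cycle table stays.

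2. Separately, the sponsor should reconcile Tables 1 and 2 with each other and with the recovery statement in Section 4.3.1, or state why the count days differ. Which monitoring days are right is for the sponsor to decide.
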